4. STUDY DESIGN

4.1. Overall Design

Study 207966 (Antiretroviral Therapy as Long Acting Suppression every 2 Months-ATLAS-2M) is a Phase III, randomized, open-label, active-controlled, multicenter, parallel-group, non-inferiority study designed to assess the antiviral activity and safety of CAB LA + RPV LA administered every 4 weeks compared CAB LA + RPV LA administered every 8 weeks in approximately 1020 adult HIV-1 infected patients.

Two groups of patients who fulfill eligibility requirements will be randomized (1:1) at Day 1 to receive CAB LA + RPV LA Q4W, or CAB LA + RPV LA Q8W regimen for at least 100 weeks:

Group 1: Patients randomized from current ART Standard of Care (SOC) therapy

Patients randomized from current ART SOC therapy, including those enrolled to the “current ART” arm of the ATLAS study following completion of the Week 52 visit (at minimum), will begin oral therapy with CAB 30 mg + RPV 25 mg once daily at Day 1 for 28 days (± 3 days) to determine individual safety and tolerability prior to receiving CAB LA + RPV LA Q4W, or CAB LA + RPV LA Q8W. For patients on SOC transitioning from the ATLAS trial, eligibility for ATLAS-2M can be determined once

the final central lab results from ATLAS are available and safety parameters have been reviewed.

Group 2: Patients currently receiving CAB LA + RPV LA Q4W

[figure not shown]
At Day 1, patients entering ATLAS-2M from ATLAS and currently receiving CAB LA + RPV LA Q4W (including both those who were originally randomized to Q4W in the Maintenance phase of ATLAS and those who transitioned from SOC to the Q4W regimen within the Extension Phase of ATLAS) will be randomized 1:1 to either continue Q4W administration or transition to Q8W administration of CAB LA + RPV LA. The first injection visit for ATLAS-2M can be performed once the final central lab results from ATLAS are available and safety parameters have been reviewed, and the ATLAS Week 52 visit (at minimum) has been completed. Participants will continue to receive CAB LA + RPV LA Q4W injections as scheduled within the ATLAS trial until their eligibility for ATLAS-2M can be fully evaluated and the participant is re-randomized (Q4W or Q8W). If determined to be ineligible for ATLAS-2M, those participants can elect to continue participation in ATLAS or withdraw from the ATLAS study.

Participants in ATLAS-2M who successfully complete Week 100 (without meeting study defined withdrawal criteria) will be given the option to continue to receive their randomized treatment (CAB LA + RPV LA administered Q4W or Q8W) in the Extension Phase until the randomized study treatment is either locally approved and commercially available within the local sector (including through local public/government health sectors), the participant no longer derives clinical benefit, the participant meets a protocol-defined reason for discontinuation or until development of either CAB LA + RPV LA Q4W and/or Q8W is terminated. Alternatively, participants can choose to complete study participation and enter the 52-week LTFU Phase of the study.

Any participant who receives at least one dose of CAB LA and/or RPV LA and discontinues the CAB LA + RPV LA regimen for any reason will enter a 52-week LTFU Phase. Those participants must remain on suppressive highly active antiretroviral therapy (HAART) for at least 52 weeks after the last dose of CAB LA and/or RPV LA.

In order to achieve balance across the treatment arms, randomization will be stratified by prior CAB + RPV Exposure: 0 weeks, 1-24 weeks, >24 weeks. The primary endpoint for the study is the proportion of participants with HIV-RNA greater than or equal to 50 c/mL (Virologic Failure) at Week 48 as per Food and Drug Administration (FDA) Snapshot algorithm using the Intent-to-Treat Exposed (ITT-E) population. The proportion of participants with plasma HIV-1 RNA <50 c/mL at Week 48 using the FDA Snapshot algorithm (Missing, Switch or Discontinuation = Failure, ITT-E population) is a key secondary endpoint comparison.

The sample size of 1020 provides 85% power to demonstrate non-inferiority in the primary endpoint at Week 48 using a 4% margin, assuming a true 3% failure rate for Q8W CAB LA + RPV LA and a 2% failure rate for the Q4W CAB LA + RPV LA arm and a 2.5% one-sided alpha level.

Figure 1 207966 (ATLAS-2M) Study Design Schematic

N=1020, randomized 1:1 to each arm and stratified by prior CAB + RPV Exposure

SOC Patients not transitioning from the ATLAS study must be on uninterrupted current regimen (either the initial or second cART regimen) for at least 6 months prior to Screening. Documented evidence of at least two plasma HIV-1 RNA measurements <50 c/mL in the 12 months prior to Screening: one within the 6 to 12 month window, and one within 6 months prior to Screening. No history of virologic failure. No evidence of viral resistance based on the presence of any resistance-associated major INI, or NNRTI mutation (except K103N) from prior genotype assay results. No current or prior history of etravirine use.

†Optional Extension Phase to continue randomized CAB LA + RPV LA Q4W or Q8W at Wk 100

‡Participants who withdraw from IM regimen must go into 52 week long term follow up phase if randomized regimen is not yet locally approved and commercially available.

4.2. Treatment Groups and Duration

4.2.1. Screening Phase (Up to 35 days)

Informed consent must be obtained prior to any study procedures, including any Screening assessment.

Participants will be involved in a Screening period of up to 35 days and may be re-screened once. Participants who are randomized into the trial and subsequently withdrawn from the study, for any reason, may not be re-screened. Participants may be randomized as soon as all eligibility requirements have been confirmed at the site.

For participants transitioning from the ATLAS study, eligibility to transition to ATLAS-2M at Week 52 (at the earliest) will be determined once the final central lab results from ATLAS, following (at minimum) completion of the ATLAS Week 48 visit are available and safety parameters have been reviewed. Separate Screening Labs will be utilized to inform eligibility for ATLAS-2M; however, in some occasions and upon consultation with the Medical Monitor, individual lab results and safety data from the final visit of the ATLAS study can be considered towards informing eligibility for the ATLAS-2M study as long as all other Screening and eligibility criteria are met.

[figure not shown]
4.2.2. Maintenance Phase (Day 1 up to Week 100)

There are two ways in which study participants may transition to the LA regimen, either directly from oral SOC or from Q4W dosing from ATLAS.

Table 1 and Figure 2 describe the CAB LA + RPV LA dosing regimens in ATLAS-2M based on the mode of transition.

Table 1 CAB LA + RPV LA Dosing Regimens in ATLAS-2M

Participants Transitioning from Oral Standard of Care (SOC)		
Regimen	CAB LA	RPV LA
Q4W	CAB LA: Week 4b: 600 mg (Loading Dose) Week 8 & Q4W thereafter: 400 mg	RPV LA: Week 4b: 900 mg (Loading Dose) Week 8 & Q4W thereafter: 600 mg
Q8W	CAB LA: Week 4b, Week 8, & Q8W thereafter: 600 mg	RPV LA: Week 4b, Week 8, & Q8W thereafter: 900 mg
Participants Transitioning from ATLAS Q4W		
Regimen	CAB LA	RPV LA
Q4W	CAB LA: Day 1 & Q4W thereafter: 400 mg	RPV LA: Day 1 & Q4W thereafter: 600 mg
Q8W	CAB LA: Day 1 & Q8W thereafter: 600 mg	RPV LA: Day 1 & Q8W thereafter: 900 mg
All participants entering ATLAS-2M from an oral SOC regimen will receive a 4-week oral lead-in of CAB+RPV prior to receiving IM injections, except for ATLAS subjects transitioning from Q4W to Q8W injections. These participants previously established safety and tolerability of CAB + RPV within the ATLAS study.		

Figure 2 ATLAS-2M Treatment Schematic

4.2.2.1. Patients randomized to LA dosing from current ART SOC therapy:

All participants randomized from current ART SOC therapy (including those transitioning from SOC in ATLAS and new study participants) will begin oral therapy with CAB 30 mg + RPV 25 mg once daily at Day 1 for 4 weeks to determine individual safety and tolerability prior to administration of CAB LA + RPV LA. The oral lead-in period is part of the Maintenance Phase and will therefore be included within the 48 and 96 week analyses.

The final dosing of current daily oral ART regimen should occur the day prior to randomization to avoid overlap of treatment regimens however, if the participant takes current ART prior to coming into the clinic, randomization and initiation of oral CAB and RPV should continue as planned for Day 1. At the Week 4a visit, safety assessments (including e.g., clinical chemistries) will be performed as per the Time and Events Table to determine individual safety and tolerability prior to the initial administration of CAB LA + RPV LA. Dosing of CAB LA + RPV LA Q4W or Q8W will initiate at the Week 4b visit once safety labs from Week 4a are available and have been reviewed.

Subjects receiving oral SOC treatment and randomized to Q4W injections will receive loading doses of CAB LA 600 mg + RPV LA 900 mg on **Week 4b** followed by maintenance injections of CAB LA 400 mg + RPV LA 600 mg every 4 weeks thereafter.

Subjects receiving oral SOC treatment and randomized to Q8W injections will receive doses of CAB LA 600 mg + RPV LA 900 mg on **Week 4b and Week 8** followed by identical maintenance dose injections every 8 weeks thereafter.

All injections should be planned as single injections per drug.

4.2.2.1.1. IM injections every 4 weeks (Q4W from SOC):

Week 4b visit only - CAB LA 600 mg + RPV LA 900 mg, each given as 1 X 3 mL IM injection

Week 8 visit and Q4W thereafter - CAB LA 400 mg IM + RPV LA 600 mg IM every 4 weeks for 100 weeks, each given as 1 X 2 mL IM injection

At Week 4b, participants will return to the clinic, take the last oral dose (CAB 30 mg + RPV 25 mg), and receive the first CAB LA (600 mg) + RPV LA (900 mg) injections (within 2 hours of the final oral dose of CAB + RPV). The first injections with IM CAB LA + RPV LA at Week 4b can be performed once central lab results are available and safety parameters are reviewed from the Week 4a visit.

The second and third IM injections with CAB LA 400 mg and RPV LA 600 mg will be performed at Week 8 and Week 12. There will be a -7-day dosing window for the second and third IM injections such that the second injection occurs within the window of Week 7 and Week 8 but no later than Week 8 and the third injection occurs within the window of Week 11 and Week 12 but no later than Week 12. Subsequent injections with CAB LA 400 mg and RPV LA 600 mg will occur every 4 weeks (± 7 days) thereafter. In addition, starting after the Week 16 injection, the interval between injection visits will be limited to a maximum of 5 weeks. The Medical Monitor must be contacted to discuss individual participant case management if the length of time between injections exceeds or is projected to exceed 5 weeks.

4.2.2.1.2. IM injections every 8 weeks (Q8W from SOC):

Week 4b visit – CAB LA 600 mg + RPV LA 900 mg IM, each given as 1 X 3 mL IM injection

Week 8 visit- CAB LA 600 mg + RPV LA 900 mg IM, each given as 1 X 3 mL IM injection

Week 16 visit and Q8W thereafter - CAB LA 600 mg + RPV LA 900 mg IM, every 8 weeks for 100 weeks, each given as 1 X 3 mL IM injection

At the Week 4b visit, subjects will return to the clinic, take their last oral dose (CAB 30 mg + RPV 25 mg), and receive the first CAB LA (600 mg) + RPV LA (900 mg) injections (within 2 hours of the final oral dose of CAB + RPV). The first injections with IM CAB LA + RPV LA at Week 4b can be performed once central lab results are available and safety parameters are reviewed from the Week 4a visit.

The second loading injection will be administered at Week 8 (CAB LA 600 mg + RPV LA 900 mg, with subsequent injections (CAB LA 600 mg + RPV LA 900 mg) occurring every 8 weeks thereafter. There will be a -7-day dosing window for the second and third IM injections such that the second injection occurs within the window of Week 7 and Week 8 but no later than Week 8 and third injection occurs within the window of Week

15 and Week 16 but no later than Week 16. Subsequent injections with CAB LA 600 mg and RPV LA 900 mg will occur every 8 weeks (± 7 days). Starting after the Week 16 injection, the interval between injection visits will be limited to a maximum of 9 weeks. If the length of time between injections exceeds, or is projected to exceed 9 weeks, the Medical Monitor must be contacted to discuss individual participant case management.

4.2.2.2. Participants transitioning from ATLAS and currently receiving CAB LA + RPV LA Q4W

Subjects receiving Q4W injections within ATLAS and randomized to receive Q4W injections in Study 207966 will continue receiving maintenance injections Q4W as scheduled and will not require a loading dose on Day 1.

Subjects receiving Q4W injections within ATLAS and randomized to receive Q8W injections in Study 207966 will receive doses of CAB LA 600 mg + RPV LA 900 mg on Day 1, one month after their last Q4W maintenance dose, in order to align with Day 1 of study randomization. Subjects will not require an intermediate dose at Week 4 and will receive their next Q8W maintenance injections at Week 8 and Q8W thereafter.

Participants transitioning from the ATLAS study and on CAB LA + RPV LA Q4W treatment will be randomized at Day 1 to either continue Q4W administration or transition to Q8W administration of CAB LA + RPV LA. The first injection visit for the ATLAS-2M study can be performed once the final central lab results from the ATLAS study are available and safety parameters have been reviewed. Screening labs determining eligibility for ATLAS-2M can be collected at Week 48 (at minimum) for participants originally randomized to the Q4W arm within ATLAS. Screening labs for participants who transitioned from SOC to Q4W injections within the ATLAS Extension Phase may be obtained at ATLAS Week 56b (following the CAB + RPV Oral lead-in period) or at subsequent ATLAS visits after receiving one set or a short course of Q4W injections. The transition from the final ATLAS to ATLAS-2M Day 1 dosing must occur 4 weeks (± 7 days) from the final injections received in ATLAS

Dosing for participants transitioning from CAB LA + RPV LA Q4W in ATLAS is as follows:

4.2.2.2.1. IM injections every 4 weeks (Q4W from ATLAS Q4W):

Starting at Day 1, all injections will continue with maintenance doses of CAB LA 400 mg and RPV LA 600 mg administered every 4 weeks (± 7 days). In addition, the time between injection visits will be limited to a maximum of 5 weeks. The Medical Monitor must be contacted if the length of time between injections exceeds or is projected to exceed 5 weeks.

4.2.2.2.2. IM injections every 8 weeks (Q8W from ATLAS Q4W):

Participants transitioning from ATLAS and randomized to receive CAB LA + RPV LA Q8W injections will initiate Q8W dosing at the Day 1 visit as follows:

Day 1- CAB LA 600 mg + RPV LA 900 mg IM, each given as 1 X 3 mL IM injection

Week 8 and Q8W thereafter- CAB LA 600 mg + RPV LA 900 mg IM, each given as 1 X 3 mL IM injection

The second loading injection will be administered at Week 8 (CAB LA 600 mg + RPV LA 900 mg), with subsequent injections (CAB LA 600 mg + RPV LA 900 mg) occurring every 8 weeks thereafter. There will be a -7-day dosing window for the second and third IM injections such that the second injection occurs within the window of Week 7 and Week 8 but no later than Week 8 and third injection occurs within the window of Week 15 and Week 16 but no later than Week 16. Subsequent injections with CAB LA 600 mg and RPV LA 900 mg will occur every 8 weeks (± 7 days). Starting after the Week 16 injections, the interval between injection visits will be limited to a maximum of 9 weeks. If the length of time between injections exceeds, or is projected to exceed 9 weeks, the Medical Monitor must be contacted to discuss individual participant case management.

The primary study analysis will consist of data collected through the Week 48 visit. A single repeat of HIV-1 RNA for any participant with a HIV-1 RNA ≥ 50 c/mL at Week 48 or Week 96 must be performed. The retest should be scheduled as soon as possible (but no later than 4 weeks from the Week 48 or Week 96 visits, respectively) and will inform the Week 48 or Week 96 virological endpoint, respectively.

4.2.3. Extension Phase

Participants who successfully complete 96 Weeks of CAB LA + RPV LA treatment in the Maintenance Phase will continue to have access to their randomized treatment Q4W or Q8W CAB LA + RPV LA in the Extension Phase until study treatment is either locally approved and commercially available within the local sector (including through local public/government health sectors), the participant no longer derives clinical benefit, the participant meets a protocol-defined reason for discontinuation or until development of either CAB LA + RPV LA Q4W and/or Q8W is terminated. For participants randomized to Q4W arm, dosing visits will continue to occur every 4 weeks with CAB LA 400 mg and RPV LA 600 mg. For participants randomized to the Q8W arm, dosing visits will continue to occur every 8 weeks with CAB LA 600 mg and RPV LA 900 mg. Safety and efficacy assessments will be conducted as per the Time and Events Schedule.

Participants choosing to not enter the Extension phase can complete their study participation at the Week 100 visit and enter into the LTFU Phase as required.

Participants who choose to continue on to the Extension Phase will need to be assessed for eligibility and will continue on their current CAB LA + RPV LA regimen while eligibility is being confirmed. A single repeat of HIV-1 RNA for any participant with a HIV-1 RNA ≥ 50 c/mL and < 400 c/mL at Week 96 must be performed. The retest should be scheduled as soon as possible (but no later than 4 weeks from the Week 96 visit). Participants with HIV-1 RNA < 50 c/mL upon retest are eligible to enter the Extension Phase. Participants with HIV-1 RNA ≥ 400 c/mL at Week 96 are not eligible to enter the Extension Phase, will not be allowed a repeat to determine eligibility, and will therefore be withdrawn from the study. Eligibility to enter the Extension Phase for any participants

with a retest HIV-1 RNA >50 c/mL and <400 c/mL will require approval by the study Medical Monitor.

Participants not eligible to enter the Extension Phase or choosing not to participate in the Extension Phase will end their study treatment and enter the LTFU Phase until/unless the Follow-Up Phase is no longer required based on local approval of the assigned CAB LA + RPV LA regimen. Sites may be reimbursed for up to a one-month supply of antiretroviral medication to facilitate transition to non-study ART for participants that do not qualify for the Extension Phase.

4.2.4. LTFU Phase – IM Regimen Only

Any participant who receives at least one dose of CAB LA and/or RPV LA and discontinues the CAB LA + RPV LA regimen for any reason must remain on suppressive HAART for at least 52 weeks after the last dose of CAB LA and/or RPV LA in order to prevent selective pressure on HIV and the potential for selection of resistant mutants. **Investigators must discuss the choice of the follow-up HAART regimen with the Medical Monitor prior to initiating the new regimen with the participant. HAART therapy should be initiated within 4 weeks (\pm 7 days) after the last Q4W injection, or within 8 weeks (\pm 7 days) after the last Q8W injection.** The LTFU will begin the day of the last CAB LA and/or RPV LA dose and continue for 52 weeks, or until the assigned CAB LA + RPV LA regimen is locally approved and commercially available. These participants will complete Withdrawal assessments and will then enter into the LTFU as per the Time and Events Schedule. In addition, for participants who withdraw during the LTFU, the final visit will be considered the study withdrawal visit.

Participants will be assessed with clinic visits at months 3, 6, 9, and 12 during the LTFU Phase. Female participants of child bearing potential must continue to use adequate contraception methods (see Study Procedures Manual for list of accepted forms of contraception) for the entire year of follow up.

In order to assure that participants have access to HAART during the LTFU, GSK may supply HAART regionally or reimbursement will be provided as needed during this phase. The LTFU Phase may be shortened or terminated at any time during the study for various reasons, e.g., better understanding of risks of development of resistance as CAB and RPV exposures decline, regulatory approval and commercial availability, end of study timings, etc.

This phase is considered study participation and participants will be followed on study during this time. A withdrawal visit is not required for participants who do not complete the LTFU Phase. The participants' last on study visit will be considered as their withdrawal visit.

4.2.5. Dose Modifications:

No dose reductions, modifications, or changes in the frequency of any components of each regimen will be allowed during the study beyond what is allowed within the protocol or directly approved by the study Medical Monitor. Protocol waivers or

exemptions are not allowed. Therefore, adherence to the study design requirements is essential and required for study conduct.

In exceptional circumstances, and in consultation with the Medical Monitor, Investigators may provide oral CAB and/or RPV as a short-term “bridging” strategy for participants who have begun CAB LA + RPV LA (see Section 6.8.1 for additional details). Should a participant need “oral bridging”, sites must contact the Medical Monitor for guidance on treatment strategies prior to a missed CAB LA + RPV LA dose. Should a participant not notify the site in advance, the Medical Monitor must be contacted for further treatment guidance.

Supplementary study conduct information not mandated to be present in this protocol is provided in the accompanying Study Procedures Manual (SPM), which is available on the online Study Web Portal. The SPM will provide the site personnel with administrative and detailed technical information.

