1.4.4. Long-Term Follow-Up Phase

Any participant who receives at least one dose of CAB LA and/or RPV LA and discontinues the CAB LA + RPV LA regimen for any reason must remain on suppressive HAART for at least 52 weeks after the last dose of CAB LA and/or RPV LA in order to prevent selective pressure on HIV and the potential for selection of resistant mutants. **Investigators must discuss the choice of the follow-up HAART regimen with the Medical Monitor prior to initiating the new regimen with the participant. HAART therapy should be initiated within 4 weeks after the last Q4W injection, or within 8 weeks after the last Q8W injection.** The LTFU will begin the day of the last CAB LA and/or RPV LA dose and continue for 52 weeks, or until the assigned CAB LA + RPV LA regimen is locally approved and commercially available. Upon discontinuation from the Maintenance or Extension Phase, these participants will complete Withdrawal assessments (see Section 5.5) and will then enter into the LTFU as per the Time and Events Schedule (Section 7.1).

Participants will be assessed with clinic visits at months 3, 6, 9, and 12 during the Follow-Up Phase. Female participants of child bearing potential must continue to use adequate contraception methods (see Study Procedures Manual for list of accepted forms of contraception) for the entire year of follow up.

In order to assure that participants have access to HAART during the LTFU, GSK may supply HAART regionally or reimbursement will be provided as needed during this phase. The LTFU Phase may be modified or terminated at any time during the study for various reasons, e.g., better understanding of risks of development of resistance as CAB and RPV exposures decline, regulatory approval and commercial availability, end of study timings, etc.

This phase is considered study participation and participants will be followed on study during this time. Additional withdrawal assessments are not required for participants who do not complete the LTFU Phase.

1.4.5. Dose Modifications:

No dose reductions, modifications, or changes in the frequency of any components of each regimen will be allowed during the study beyond what is allowed within the protocol or directly approved by the study Medical Monitor. Protocol waivers or exemptions are not allowed. Therefore, adherence to the study design requirements is essential and required for study conduct.

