	
established at the mid dose 5 mg/kg/day, the maternal exposure at this dose calculated using systemic exposure from non-pregnant rats is >20 fold predicted Cmax and AUC exposures for anticipated clinical CAB LA exposures for HIV treatment
 
The clinical significance in humans of these findings is unknown.
	
throughout the long term follow up phase of this study following exposure to CAB LA.
 
 FRP are also required to undergo regular pregnancy testing throughout study conduct to enable early discontinuation of CAB LA once pregnancy is identified.

Development of Resistance following discontinuation of CAB LA
	
Residual concentrations of CAB would remain in the systemic circulation of participants who stop CAB LA treatment for prolonged periods (more than 1 year, in some subjects, GlaxoSmithKline Document Number 2016N269422_00) after last injection (e.g., for tolerability issues or treatment failure). Participants discontinuing CAB LA regimen may be at risk for developing HIV-1 resistance to CAB many weeks after discontinuing injectable therapy.
	
 After participants stop CAB LA, Oral HAART regimens will be prescribed within 4 weeks after the last Q4W dose or within 8 weeks after the last Q8W dose, and following consultation with the medical monitor. This would be anticipated to result in continued suppression or rapid resuppression of HIV-1 RNA thus minimizing the risk of emergent resistance The participants in this study who discontinue IM CAB for any reason will be monitored for a minimum of 52 weeks from the time of the last IM CAB injection.

Potential Risk of Clinical Significance	Summary of Data/Rationale for Risk	Mitigation Strategy

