4.5.2.1. CAB LA Q8W

The CAB LA 600mg Q8W regimen is predicted to achieve concentrations above 1.35 µg/mL, the geometric mean C_{τ} following oral CAB 10 mg once daily which was shown to be efficacious in the LATTE study. The lower bound of the 90% prediction interval is approximately 0.166 µg/mL, indicating that 95% of subjects on this regimen should remain above the PA-IC₉₀ throughout dosing (Figure 4). The CAB LA Q8W regimen consists of identical 600 mg doses administered at Day 1, Week 4, and Q8W thereafter.

Figure 4 Simulated* Median (90% Prediction Interval [PI]) CAB Plasma Concentrations versus Time for the Optimized CAB LA Q8W Regimen (600 mg IM Day 1, Week 4, Q8W Thereafter)^

*Note: current simulations based on interim plasma concentration dataset

^Study Time and Events include a 4-week oral lead in for subjects transitioning to Q8W from oral SOC. Therefore, Day 1 (time zero) = date of first injections in 207966

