4.5.3.1. RPV LA Q8W

The RPV LA Q8W regimen for this study (ATLAS-2M) was selected based on safety and efficacy data from study 200056 (LATTE-2) and supported by modeling and simulation of pharmacokinetic data obtained following administration RPV LA administration in healthy subjects (Phase 1 studies C158, and LAI115428 [GlaxoSmithKline Document Number [2011N112455_03](#)]) and in HIV-infected subjects (Phase 2 study LATTE-2), the majority of the data coming from 200056 (LATTE-2).

The RPV LA 900 mg Q8W regimen is predicted to achieve median (90% PI) steady-state C_{τ} of 54 ng/mL (23 – 112 ng/mL) (Figure 10). With this regimen, 100% of subjects remain above the RPV PA-IC₉₀ during the whole dose interval at steady-state. These data are similar to the observed Week 32 median steady-state C_{τ} in LATTE-2 for Q8W which was also 54 ng/mL and the mean C_{τ} was 58 ng/mL. The RPV LA Q8W regimen consists of identical 900 mg doses administered at Day 1, Week 4, and Q8W thereafter. With the second RPV LA dose administered 4 weeks after the first dose, the anticipated median RPV C_{τ} at Week 4 (prior to second injection) is 40 ng/mL (versus 30 ng/mL observed prior to second injection at Week 8 in LATTE-2, where the RPV LA dose at Week 4 was not included), with >92% of subjects above the RPV PA-IC₉₀ of 12 ng/mL.

Figure 10 Simulated* Median (90% PI) RPV Plasma Concentrations versus Time Profile for the Optimized RPV LA Q8W regimen (900 mg IM Day

* Note: current simulations based on interim plasma concentration dataset

[figure not shown]
^Study Time and Events include a 4 week oral lead in for subjects transitioning to Q8W from oral SOC. Therefore, Day 1 = date of first injections for Study 207966

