4.5.3.2. RPV LA Q4W

[figure not shown]
The RPV LA Q4W regimen for ATLAS-2M was selected based on LATTE-2 safety and efficacy data as described above and supported by modeling and simulation of pharmacokinetic data as described above. The Q4W dose regimen consists of a RPV LA 900 mg dose on Day 1, and RPV LA 600 mg every 4 weeks thereafter. This regimen is also studied in the Phase 3 studies ATLAS and FLAIR.

There are two ways in which study participants may transition to the Q4W regimen, either directly from oral SOC or directly from Q4W dosing from ATLAS. Figure 14 shows the predicted plasma RPV PK profile for SOC participants directly transitioning to

Q4W dosing following completion of the oral lead-in phase. Former ATLAS participants receiving Q4W injections and randomized to the Q4W dosing arm of ATLAS-2M will continue receiving Q4W injections as scheduled.

The predicted median (90% PI) steady-state C_{τ} for the proposed regimen is 84 ng/mL (41 – 161 ng/mL, [Figure 14](#)). With this regimen, >99% of participants remain above the 5th percentile of steady state trough values following oral RPV 25 mg (corresponding to 2x the PA-IC₉₀). With a loading dose of 900 mg RPV LA on Day 1, the anticipated median RPV C_{τ} at Week 4 is 40 ng/mL, with >92% of participants above the RPV PA-IC₉₀.

Figure 14 Simulated* Median (90% PI) RPV Plasma Concentrations versus Time Profile for the RPV LA Q4W regimen (900 mg IM Day 1, then 600 mg IM Q4W thereafter^)

* Note: current simulations based on interim plasma concentration dataset

^Study Time and Events include a 4-week oral lead in. Therefore, Day 1 = day of first injections for Study 207966

At steady-state, a one-week delay in dosing for the Q4W regimen is predicted to result in a median steady-state C_{τ} that remains above the median trough for oral RPV 25 mg once daily. This supports allowance of some flexibility in the dosing regimen, as also practiced in LATTE-2 and the Phase 3 studies FLAIR and ATLAS.

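### The deadline for starting HAART after the last injection is stated two ways, and it lets Q8W participants from oral SOC who stop after Week 4b wait 4 to 5 weeks past their next due injection

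*Protocol*

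**What the plan says.** **HAART start.** The current text sets the limit in three places.

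- Section 1.4.4 (synopsis): "HAART therapy should be initiated within 4 weeks after the last Q4W injection, or within 8 weeks after the last Q8W injection". There is no tolerance.
- Section 2.3.1, in both the CAB LA and the RPV LA resistance entries: "Oral HAART regimens will be prescribed within 4 weeks after the last Q4W dose or within 8 weeks after the last Q8W dose". There is no tolerance, and the verb concerns prescribing rather than starting.
- Section 4.2.4: the same 4 and 8 weeks, each with plus or minus one week. The Q8W limit ends "7 days) after the last Q8W injection".

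**Injections for participants from oral SOC.** Section 4.2.2.1.1 gives the Q4W arm's first injection: "Week 4b visit only - CAB LA 600 mg + RPV LA 900 mg, each given as 1 X 3 mL IM injection". Section 4.2.2.1.2 gives the Q8W arm the same two doses at Week 4b. For the second Q8W injection it allows Week 7 to Week 8, "but no later than Week 8 and third injection" and so on. Section 6.9.1.2 softens this to a preference. The dose justification has the same spacing, counted from the first injection: "The CAB LA Q8W regimen consists of identical 600 mg doses administered at Day 1, Week 4, and Q8W thereafter" (Section 4.5.2.1), and for RPV LA "identical 900 mg doses administered at Day 1, Week 4, and Q8W thereafter" (Section 4.5.3.1).

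**Withdrawal visit.** When the decision falls between clinic visits, Section 5.5 allows the withdrawal visit up to 4 weeks (Q4W) or 8 weeks (Q8W) after the last injection. It requires that visit to come before the next ART regimen starts.

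**Purpose.** The amendment summary explains the window in Section 4.2.4 as a way to make HAART begin at about the time drug coverage ends.

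**The concern.** There are two faults.

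First, the latest permitted HAART start differs by a week depending on which section a site reads.

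Second, and more important, the limit takes the arm's maintenance interval as the length of cover from any injection in that arm. That is wrong for the Week 4b injection in the Q8W arm, because the Q8W regimen from oral SOC has a 4-week gap between its first and second injections. A participant who stops in that gap falls under an 8-week limit although the next dose was due at about 4 weeks.

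Section 2.3.1 names resistance after stopping as a risk for both drugs and relies on prompt HAART to limit it. The rule is therefore loosest, relative to the dosing schedule, for people who have had one injection and are not at steady state. No effect on the primary endpoint or on the planned resistance endpoint is claimed.

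**Working it through.** No power or error-rate figure is involved. The check is interval arithmetic on the stated schedule.

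**Inputs**

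- HAART limit: 4 weeks (Q4W) or 8 weeks (Q8W) in Sections 1.4.4 and 2.3.1. Adding the one-week tolerance in Section 4.2.4 makes the latest dates 5 and 9 weeks.
- Next injection after Week 4b, participants from SOC, either arm: by Week 8, about 4 weeks later (Sections 4.2.2.1.1 and 4.2.2.1.2).
- Next injection after Day 1, ATLAS Q4W participants moving to Q8W: Week 8, with no intermediate dose (Section 4.2.2.2).
- Next injection after the Week 8 injection, Q8W from SOC: Week 16, 8 weeks later (Section 4.2.2.1.2).

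**Formula:** permitted overrun = HAART limit − weeks until the next injection is due.

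| Participant and last injection | Next due (weeks) | Overrun, 1.4.4 and 2.3.1 | Overrun, 4.2.4 |
|---|---|---|---|
| Q8W from SOC, Week 4b | 4 | 8 − 4 = **4** | 9 − 4 = **5** |
| Q4W from SOC, Week 4b | 4 | 4 − 4 = 0 | 5 − 4 = 1 |
| ATLAS Q4W moving to Q8W, Day 1 | 8 | 8 − 8 = 0 | 9 − 8 = 1 |
| Q8W from SOC, Week 8 | 8 | 8 − 8 = 0 | 9 − 8 = 1 |

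Only the first row is out of line. The two SOC rows involve the identical injection, so the 8 − 4 = 4 week difference in the limit comes from the arm label alone.

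**Does the protocol's own PK support a longer limit in the Q8W arm?** For RPV at 4 weeks after the first injection it predicts the same level in both arms. Section 4.5.3.1 gives a median of 40 ng/mL, with more than 92% of participants above the PA-IC90 of 12 ng/mL. Section 4.5.3.2 gives the same two figures for Q4W (the sentence beginning "With a loading dose of 900 mg RPV LA on Day 1, the anticipated median RPV"). At Q8W steady state, Section 4.5.3.1 predicts 100% above the PA-IC90. So the model's margin is smaller after the first injection than at steady state, and it is equal between arms.

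**What is known at 8 weeks after one injection?** For RPV, Section 4.5.3.1 reports 30 ng/mL before the Week 8 injection in LATTE-2, where RPV LA was not given at Week 4. That is 30/12 = 2.5 times the PA-IC90, with no spread given. For CAB the protocol has no figure: the LATTE-2 Q8W arm received CAB LA at Week 4 (Section 4.5.2).

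**The case against.** **The tolerance mismatch is editorial.** Section 4.2.4 is the full text and Section 1.4.4 its synopsis. Section 2.3.1 speaks of prescribing, and the difference is at most one week. This stands as far as it goes: the mismatch is the smaller part of the point.

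**The limit attaches to a Q8W injection, and Week 4b is a loading dose.** Table 7 in Section 6.3 labels it as loading and lists the Q8W maintenance injections separately. This does not hold. Section 4.2.2.1.2 lists Week 4b under the Q8W schedule, and Table 1 and Sections 4.5.2.1 and 4.5.3.1 count the first dose as part of the Q8W regimen. If the narrow reading were right, that injection would have no HAART limit at all, which is no better.

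**Other safeguards make a long wait unlikely.** The limits are ceilings. The HAART choice must be discussed with the Medical Monitor (Section 4.2.4). Investigators are to ensure that alternative ART is started (Section 6.9.1). Oral bridging exists for planned missed doses (Section 6.8.1), and missed visits prompt contact (Section 5.5). All of this is true and lowers the practical risk, but none of it sets an earlier date.

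**Harm is not shown.** This also stands in part. The LATTE-2 RPV value at 8 weeks is reassuring at the centre of the distribution, though it says nothing about the lower tail or about CAB. The group is limited to Q8W participants from SOC who stop between Week 4b and Week 8, and its size is not given.

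**The Study Procedures Manual may say more.** It is not available here, so the statement that nothing shortens the limit applies to the protocol only.

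**Conclusion.** The concern holds. The protocol gives two versions of the HAART deadline. Under either, a Q8W participant from oral SOC who stops after Week 4b may start HAART 4 weeks (5 under Section 4.2.4) after the next injection was due. A Q4W participant given the same injection has 0 (1).

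For this group the rule misses its stated aim of matching drug coverage. ATLAS rollovers on Q8W and participants at steady state are not materially affected.

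The conclusion assumes that the Week 4b injection counts as a Q8W injection, as Section 4.2.2.1.2 presents it, and that Week 4b falls about 4 weeks before Week 8. The extent of under-exposure, the added resistance risk and the number of participants cannot be quantified from the protocol. This should be corrected as a safety rule.

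**What to change.** Use one rule in Sections 1.4.4, 2.3.1 and 4.2.4: HAART starts no later than the date the next injection would have been due, with the dosing window allowed for that injection. State that for a Q8W participant from oral SOC whose only injection was at Week 4b, this means study Week 8, about 4 weeks after the injection. From the Week 8 injection onward the Q8W limit stays tied to the 8-week interval.

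Align the Section 5.5 limit for an unscheduled withdrawal visit with the same date, since that visit must precede the new regimen.

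The cost is protocol wording and a notice to sites. No visits or samples are added.
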